11.4.3. Replacement of Subjects

Subjects who are withdrawn from the study before receiving study drug may be replaced. Once assigned, subject numbers will not be reused; subjects enrolled to replace those who withdraw will be assigned a unique subject number.

11.5. Selection of Doses in the Study

The dose of EXPAREL (4 mg/kg) was selected to provide similar exposure in pediatric subjects as was seen in adults. A Population PK model was developed using all data obtained from the infiltration studies in adult subjects (SKY0402-C-201, SKY0402-C-208, SKY0402-C-316, SKY0402-C-317, and SKY0402-C-401). Simulations from this model were performed to predict bupivacaine plasma concentrations in pediatric subjects aged 6 to less than 17 years. The dose of EXPAREL administered will not exceed 266 mg, regardless of the weight of the subject.

The selection of the 4 mg/kg dose is also supported by real world evidence collected at the Cleveland Clinic, where 375 pediatric patients have received EXPAREL at a mean dose of 4.1 ± 1.8 mg/kg, with no significant AEs attributed to EXPAREL use.

11.6. Prior and Concomitant Therapy and Medications

All medications taken within 30 days prior to study drug administration till Day 30 after study drug administration or until the subject is withdrawn from the study, whichever is sooner, will be

recorded on the eCRF. Additionally, any medications administered in association with an AE will be recorded till Day 30.

11.6.1. Before Study Drug Administration

Permitted Prior Medications and Therapy

• Prophylactic antibiotics are permitted according to the surgeon's preference.

Restricted Prior Medications and Therapy

• Use of an investigational drug within 30 days or 5 elimination half-lives of such investigational drug, whichever is longer, prior to study drug administration, or planned administration of another investigational product or procedure during the subject's participation in this study is not permitted.

11.6.2. During Surgery

Permitted

• Use of intraoperative opioids, acetaminophen, ketorolac, or other NSAIDs.

Restricted

- No drugs should be admixed with the study drug (e.g., epinephrine, dexamethasone, clonidine).
- Avoid additional use of local anesthetics within 96 hours following administration of EXPAREL.

11.6.3. After Surgery

Permitted

- Postsurgical pain management will consist of institution's standard of care in case of insufficient analgesia.
- Parenteral antiemetic medication may be administered, as needed.

Restricted

• Avoid additional use of local anesthetics within 96 hours following administration of EXPAREL.

All postsurgical analgesics administered must be documented till 96 hours after surgery.

11.7. Treatment Compliance

Study drug will be administered intraoperatively by the study staff and, thus, compliance is ensured.

11.8. Accountability of Study Drug

Any shipment of EXPAREL for the study will contain an investigational drug transmittal and receipt form to assist the investigator or designee (e.g., pharmacist) in maintaining current and accurate inventory records. At a minimum, the pharmacist or designee will maintain accurate records demonstrating dates and units of drug received, lot numbers, subjects to whom drug was administered, and accounts of any drug destroyed accidentally or deliberately. The investigator must retain vials containing used, unused, or expired EXPAREL for return or destruction, as instructed by Pacira, following confirmation of drug accountability data by an unblinded study monitor. A record of drug return or destruction will be maintained and provided to Pacira. Inventory records must be readily available for inspection by the unblinded study monitor and appropriate regulatory authorities at any time. A copy of the inventory records, drug accountability information, and notice of return or destruction will be returned to Pacira at the end of the study. Only authorized personnel identified by the investigator will have the ability to access and administer the drug.

12. STUDY ENDPOINTS AND MEASUREMENTS

12.1. Pharmacokinetic Analysis

A total of 8 blood samples will be collected per subject at specific time windows (Table 2) for the determination of plasma concentrations. Population PK modeling will be performed using all PK data collected during the study. The population PK model will estimate EXPAREL individual and population PK parameters and exposure, inter-individual variability of PK parameters, and intra-individual variability of bupivacaine concentrations.

12.2. Pharmacokinetic Endpoints

A population PK analysis will be performed. The following model-predicted PK endpoints will be determined:

- Area under the plasma concentration-versus-time curve (AUC)
- Maximum plasma concentration (C_{max})
- The apparent terminal elimination half-life $(t_{1/2el})$
- Apparent clearance (CL/F)
- Apparent volume of distribution (Vd/F)

12.3. Safety Assessments

The following safety measurements will be conducted at the time points specified:

• Vital signs (temperature, resting heart rate, respiratory rate, oxygen saturation, and blood pressure) at screening; upon arrival in the post-anesthesia care unit (PACU); at 2, 4, 8, 12, 24, 36, 48, 60, 72, and 96 hours after the end of study drug administration; at hospital discharge; and on Day 30.

- Neurological assessment at screening; at 2, 4, 8, 12, 24, 36, 48, 60, 72, and 96 hours after the end of study drug administration; at hospital discharge; and on Day 30 (Part 1 only, Appendix 3).
- Clinical laboratory tests (hematology, chemistry, and urinalysis) at screening; at baseline (on Day 1 prior to surgery) and at 96 hours after the end of study drug administration (see Appendix 4).
- AEs from the time the ICF is signed/assent is obtained till Day 30.

12.4. Safety Endpoints

The following safety endpoints will be assessed based on the safety measurements conducted at the specified time points:

- Change from baseline in vital signs (temperature, resting heart rate, respiratory rate, oxygen saturation, and blood pressure).
- Summary of neurological assessments (proportion of subjects who are oriented, and proportion of subjects who have any neurologic events). Note: Events identified during the neurologic assessment should be recorded as AEs.
- Change from baseline in clinical laboratory data.
- Incidence of TEAEs and SAEs till Day 30.

12.5. Other Measurements

The following efficacy measurements will be done for exploratory purposes only:

- Pain intensity scores at screening; at 4, 8, 12, 24, 36, 48, 60, 72, and 96 hours after the end of study drug administration; immediately prior to each administration of postoperative opioid pain management medication till 96 hours; and at hospital discharge. If a subject is too anesthetized at the time of a scheduled pain intensity assessment, the assessment should be skipped. Pain intensity scores will be collected using the following instruments:
 - 11-point NRS-R for subjects aged 12 to less than 17 years (Appendix 1)
 - CAS for subjects aged 6 to less than 12 years (Appendix 2)
 - Postoperative opioid pain management medication use (time, dose) till hospital discharge.

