• Pain intensity scores at screening	; at 4, 8, 12, 24, 36, 48, 60, 72, and 96 h to each administration of postoperative	nours after the end of study drug						
till 96 hours; and at hospital disch	harge. If a subject is too anesthetized at d be skipped. Pain intensity will be me	the time of a scheduled pain intensity						

Name of Sponsor/Company: Pacira Pharmaceuticals, Inc. [name] [contact]	Individual Study Table Referring to Part of the Dossier Volume: Page:	(For National Authority Use Only)
Name of Finished Product: EXPAREL		
Name of Active Ingredient: Bupivacaine, 1.3%, 13.3 mg/mL		

- 11-point NRS-R for subjects aged 12 to less than 17 years (Appendix 1)
- CAS for subjects aged 6 to less than 12 years (Appendix 2)
- Postsurgical opioid pain management medication use (time, dose) till 96 hours after the end of study drug administration.

Other Endpoints:

Analysis of other endpoints will be conducted for exploratory purposes only. The efficacy endpoints listed below will be assessed based on the efficacy measurements conducted at the time points specified.

- Pain intensity scores.
- Area under the curve (AUC) of pain intensity scores.
- Total opioid consumption in morphine equivalents.
- Time to first postsurgical use of opioid medication.

Statistical Methods:

A comprehensive statistical analysis plan will be developed for this study. Descriptive statistics (number of subjects, mean, standard deviation, median, minimum, and maximum) will be provided for continuous data. Tabulations (number and percentage of subjects) by category will be provided for categorical data. This study is not powered for efficacy.

A prospective population PK analysis plan will be developed. Nonlinear mixed-effect modeling will be used to analyze the sparse concentration-versus-time data.

Population and individual PK parameters will be estimated. Individual PK parameters estimated for each subject will be used to compute PK exposures (AUC and C_{max}). All PK parameters will be presented in listings and descriptive summary statistics, including the arithmetic mean, median, range, standard deviation, and coefficient of variation. Details and results of this mixed-effect modeling analysis will be reported separately.

Sample Size

The sample size was based on the number of subjects necessary to characterize the PK profile of EXPAREL in pediatric subjects with the precision required by the Food and Drug Administration.

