In the situation where PK blood draws and other assessments coincide or occur at about the same time, the blood draw for PK analysis must be conducted first, and the pain intensity assessment conducted second, as applicable, followed by any other assessments.

1 ECG abnormalities that are clinically significant should be recorded as AEs. May also conduct a 12-lead ECG if a subject experiences an AESI (i.e., cardiac AE or neurological AE), or an SAE; see footnote 7.

2 A baseline 12-lead ECG must be recorded prior to surgery and may be performed either at the screening visit or in the preoperative holding area on Day 1.

3 May also conduct clinical laboratory tests if a subject experiences an AESI or an SAE; see footnote 7.

4 Vital signs (temperature, resting heart rate, respiratory rate, oxygen saturation and blood pressure) will be measured after the subject has rested in a supine position for at least 5 minutes. May also measure vital signs if a subject experiences an AESI (i.e., cardiac AE or neurological AE), or an SAE; see footnote 7.

5 Pain intensity will be measured using the 11-point NRS-R for subjects aged 12 to less than 17 years (Appendix 1) and CAS for subjects aged 6 to less than 12 years (Appendix 2). The preoperative pain intensity assessment should be conducted immediately prior to each administration of postoperative opioid pain management medication till 96 hours. If a subject is too anesthetized at the time of a scheduled pain intensity assessment, the assessment should be skipped.

6 Instruct subject to discontinue prohibited medications. Record date/time of all medications starting at least 30 days prior to study drug administration till 96 hours after study drug administration. Record medications administered for treatment of an AE till Day 30.

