medical conditions that, in the opinion of the investigator, would preclude them from study participation. After the ICF is signed by the subject's legal guardian and written assent is provided by the subject (if capable), medical history, surgical history, physical examination, 12-lead electrocardiogram (ECG), vital sign measurements, neurological assessment, clinical laboratory tests (hematology, chemistry, and urinalysis), pain intensity score, urine pregnancy test for females of childbearing potential, urine drug screen and alcohol breath test will be conducted.

On Day 1, eligible subjects will receive the study drug intraoperatively at the end of surgery via local infiltration to produce local analgesia. Use of intraoperative opioids, acetaminophen, ketorolac, or other NSAIDs, will be permitted in accordance with the study site's standard of care.

Avoid additional use of local anesthetics within 96 hours following the administration EXPAREL.

There is no required length of stay in the hospital; subjects may be discharged based on the medical judgment of the treating physician. For subjects discharged from the hospital before all protocol-specified assessments till 96 hours are completed, a nurse will perform follow-up visits at the subject's home to perform the required postsurgical assessments and collect PK samples till 96 hours.

A follow-up phone call will be scheduled for all subjects on Day 7. For the assessment of AEs, a final follow-up visit will be made on Day 30 to all subjects who would have received the study drug.

Postsurgical Pain Management

Use of postsurgical pain medication in cases of insufficient analgesia will be permitted according to the institution's standard of care. The investigator must record all postsurgical pain management medications provided to the subjects till the hospital discharge.

Avoid additional use of local anesthetics within 96 hours following the administration EXPAREL.

Postsurgical Assessments

Postsurgical assessments to be conducted till 96 hours include pain intensity using the 11-point NRS-R (Appendix 1) for subjects aged 12 to less than years and the Color Analog Scale (CAS; Appendix 2) for subjects aged 6 to less than 12 years; neurological assessment (Appendix 3); clinical laboratory tests (Appendix 4); and vital signs.

AEs will be recorded from the time the ICF is signed/assent is given till Day 30.

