The use of postsurgical pain medication in cases of insufficient analgesia is permitted according to the institution's standard of care. The investigator must record all pain management medications administered during hospitalization. Avoid additional use of local anesthetics within 96 hours following administration of EXPAREL

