On Day 1, eligible subjects will receive the study drug intraoperatively at the end of surgery via local infiltration to produce analgesia. Use of intraoperative opioids, acetaminophen, ketorolac, or other NSAIDs, will be permitted in accordance with the study site's standard of care.

Avoid additional use of local anesthetics within 96 hours following the administration EXPAREL.

There is no required length of stay in the hospital; subjects may be discharged based on the medical judgement of the treating physician. For subjects discharged from the hospital before all protocol-specified assessments until 96 hours are completed, a nurse will perform follow-up visits at the subject's home to perform the required postsurgical assessments and collect PK samples until 96 hours.

A follow-up phone call will be scheduled for all subjects on Day 7. For the assessment of AEs, a final follow-up visit will be made on Day 30 to all subjects who would have received the study drug.

Postsurgical Pain Management

Use of postsurgical pain medication in cases of insufficient analgesia will be permitted according to the institution's standard of care. The investigator must record all postsurgical pain management medications provided to the subjects until the hospital discharge.

Avoid additional use of local anesthetics within 96 hours following the administration EXPAREL.

Postsurgical Assessments

Postsurgical assessments to be conducted until 96 hours include pain intensity using 11-point Numerical Rating Scale at Rest (NRS-R) for subjects aged 12 to less than 17 years and the Color Analog Scale (CAS) for subjects age 6 to less than 12 years; neurological assessment, clinical laboratory tests, and vital signs.

AEs will be recorded from the time of ICF is signed/assent is given until Day 30.

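### Opioid recording ends at hospital discharge, 96 h or Day 30 depending on the section, and the SAP's projection trigger is unclear, so totals for children discharged early may be observed, truncated or projected

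*Protocol*

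**What the plan says.** The documents give three ends for recording.

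- **Hospital discharge.** Protocol 12.5: "Postoperative opioid pain management medication use (time, dose) till hospital discharge". Protocol 9.1: "The investigator must record all postsurgical pain management medications provided to the subjects till the hospital discharge". The synopsis pain-management text has the same requirement, and SAP section 3 repeats it: "The investigator must record all postsurgical pain management medications provided to the subjects until the hospital discharge". Protocol 11.1: "The investigator must record all pain management medications administered during hospitalization".
- **96 h.** Synopsis, Other Assessments: "Postsurgical opioid pain management medication use (time, dose) till 96 hours after the end of study drug administration". Table 1 footnote 6: "Record date/time of all medications starting at least 30 days prior to study drug administration till 96 hours after study drug administration". Protocol 11.6.3: "All postsurgical analgesics administered must be documented till 96 hours after surgery". Protocol 13.5, whose heading runs to 96 h, asks for the date, time and amount of every opioid dose.
- **Day 30.** Protocol 11.6: "All medications taken within 30 days prior to study drug administration till Day 30 after study drug administration", or until withdrawal if that comes first.

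No minimum stay is set. Protocol 9.1 and 13.5 send a nurse to the home to complete assessments and PK samples to 96 h; neither home-visit text names opioid doses.

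SAP 6.9.2 sums oral morphine equivalents after surgery through 24, 48 and 72 h, from both the post-surgical pain medication page and the prior/concomitant medication page of the eCRF. SAP 6.1.1.2 projects incomplete totals. Its lead-in concerns subjects who leave the study early, its formulas concern subjects who are discharged, and 6.9.2 calls on it by last follow-up time. SAP 6.9.2.1 runs time to first opioid to 72 h, with a log-rank p-value for Group 1.

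**The concern.** The synopsis and Protocol 12.5 describe one measurement with two different ends. Section 12.5 also disagrees with itself: it wants a pain score before each postoperative opioid dose up to 96 h, but the doses themselves only up to discharge. One site could stop recording when the child goes home while another continues to 96 h, and each could point to protocol text.

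The analysis needs complete data to 72 h. The SAP rule that could bridge a gap does not say clearly to whom it applies. At stake is whether the exploratory opioid totals and the time to first opioid describe opioid use, or partly describe discharge time and the reading that each site and programmer adopted.

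**Working it through.** **Step 1: reproduce the SAP rule.** Let D(a,b) be the opioid amount used from a to b hours after surgery. For discharge at x hours, SAP 6.1.1.2 gives the 72 h total as

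- x < 36: 72 × D(0,x) / x
- 36 ≤ x < 72: D(0,x) + D(2x − 72, x)

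The SAP's own example is x = 70. The borrowed window starts at 2 × 70 − 72 = 68, so 68 to 70 h stands in for 70 to 72 h, as the SAP states. At x = 36 both branches give 2 × D(0,36), so the rule is continuous. The SAP presents 72 h as an example; for the 24 and 48 h totals I put the horizon H for 72 and H/2 for 36.

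**Step 2: what each reading gives** for a child who goes home before the horizon and stays in follow-up.

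| Site records to | Projection triggered by | Total is |
|---|---|---|
| 96 h or later | study discontinuation or last follow-up | observed |
| 96 h or later | discharge | projected, in place of data that exist |
| discharge | discharge | projected |
| discharge | study discontinuation or last follow-up | truncated; home use counts as zero |

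**Step 3: size.** The documents give neither discharge times nor opioid profiles, so both are assumed. The profiles are constant use, where D(a,b) is proportional to b − a, and use that halves every h = 48 or 24 hours, where D(a,b) is proportional to 2^(−a/h) − 2^(−b/h).

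Worked case, h = 24, 72 h total: D(0,72) = 1 − 0.125 = 0.875.

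- Discharge at 24 h: D(0,24) = 0.5. Truncated: 0.5 / 0.875 = 57%. Projected: 72 × 0.5 / 24 = 1.5, and 1.5 / 0.875 = 171%.
- Discharge at 48 h: D(0,48) = 0.75 and D(24,48) = 0.25. Truncated: 0.75 / 0.875 = 86%. Projected: (0.75 + 0.25) / 0.875 = 114%.

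Percentage of true use (constant / 48 h half-life / 24 h half-life):

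| Total | Discharge | Truncated | Projected |
|---|---|---|---|
| 72 h | 24 h | 33 / 45 / 57 | 100 / 136 / 171 |
| 72 h | 36 h | 50 / 63 / 74 | 100 / 125 / 148 |
| 72 h | 48 h | 67 / 77 / 86 | 100 / 109 / 114 |
| 72 h | 60 h | 83 / 90 / 94 | 100 / 102 / 102 |
| 48 h | 24 h | 50 / 59 / 67 | 100 / 117 / 133 |
| 24 h | 18 h | 75 / 78 / 81 | 100 / 102 / 104 |

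With recording to at least 72 h and no projection at discharge, every row is 100%. The 24 h total is touched only by discharge before 24 h.

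**Step 4: time to first opioid.** Take a child with no opioid in hospital, home at 24 h, whose first dose at 30 h goes unrecorded. The child is still in follow-up, so SAP 6.9.2.1 censors at 72 h and the event is lost. Projection does not help the total either: 72 × 0 / 24 = 0.

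**The case against.** A reader might infer that the totals would be truncated for every child discharged early. The documents do not support that. The discharge wording does not forbid later recording, and other sections require it: 11.6 to Day 30, and 11.6.3, footnote 6 and 13.5 to 96 h. Protocol 13.6 to 13.8 add discharge medications and concomitant medications at Day 7 and Day 30. The SAP draws on the concomitant-medication page and has a rule for an opioid taken after the day of discharge with no time recorded, so it expects such records. If its formulas are applied at discharge and use is falling, the error is an overcount. Truncation needs two things together: recording that stops at discharge, and projection confined to study discontinuation or last follow-up.

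A reader might also infer bias between the arms. Group 1 is randomized and open-label, so discharge times could differ by arm, but nothing in the documents shows that treatment affects length of stay. Group 2 has no comparator arm.

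Finally, these endpoints are exploratory, the study is not powered for efficacy, Protocol 15.1 plans no formal hypothesis test, and the totals are only summarized.

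All of this limits the consequence. It does not remove the contradiction: capture still depends on which section a site follows, and the projection trigger stays unclear even when capture is complete.

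**Conclusion.** The recording period is contradictory, and so is the trigger for projection. For a child discharged before the horizon, the 48 and 72 h totals may be observed, truncated or projected depending on the reading; the 24 h total is exposed only if discharge comes before 24 h. A first opioid taken at home may be missed.

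Across the assumed profiles, truncation leaves 33% to 57% of the 72 h total for discharge at 24 h and 67% to 86% at 48 h. Projection gives 100% to 171% and 100% to 114%. These figures illustrate the range; they do not predict this trial's data, and the direction of error depends on the reading. The documents establish neither systematic undercounting nor bias between arms. The point concerns exploratory endpoints; the primary PK and secondary safety objectives are not affected.

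**What to change.** 1. Adopt one end for opioid recording: the 96 h already in the synopsis Other Assessments, Table 1 footnote 6 and Protocol 11.6.3. Put it in the synopsis pain-management text, Protocol 9.1, 11.1 and 12.5, and SAP section 3. Name one starting point for the clock, since the synopsis and footnote 6 count from study drug and 11.6.3 from surgery.
2. Reconcile it with the Day 30 rule for all medications in 11.6.
3. State that the home nurse visits already planned to 96 h collect the time and dose of opioids taken after discharge.
4. In SAP 6.1.1.2, replace discharge by last opioid follow-up, and align the lead-in and 6.9.2, so that projection applies only when opioid follow-up ends before the horizon. Without this step, a programmer could still project over complete data.

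The cost is wording in both documents and one data item at visits that are already scheduled.
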